### 3.3.3 CRITERIA FOR RANDOMISATION

Blood samples will be taken at week 22 to assess whether the participant can proceed to randomisation. Eligibility must be assessed within 14 days prior to randomisation. If necessary it is permitted for the week 22 visit to be repeated, however it is likely that most participants will meet all eligibility criteria and be randomised around week 23. Randomisation will take place once the participant meets the following eligibility criteria:

1. Participant is willing to continue on combination antiretroviral therapy
2. HCV RNA or HCV antigen negative

---

\*\* eGFR is calculated using CKD-EPI. Units ml/min/1.73m^2.

3. Undetectable plasma HIV RNA (<50copies/mL or <200copies/mL for the Taqman Roche 2.0 assay).

Participants who do not have undetectable plasma HIV RNA at week 22 can have this repeated until the HIV RNA falls below the specified threshold. The time period between and the number of repeat tests performed will be at the clinician's discretion and up until virological failure in accordance with standard BHIVA guidelines. If it takes more than 14 days (after week 22) to become undetectable it would be necessary to repeat the whole week 22 visit prior to randomisation.

4. Laboratory parameters††
  - Platelet count  $\geq 150 \times 10^9/L$
  - eGFR  $\geq 60^{**}$
  - Adequate haemoglobin (Hb  $\geq 12g/dL$  for males,  $\geq 11g/dL$  for females)
  - ALT  $< 5 \times ULN$
  - uPCR  $\leq 30mg/mmol$
  - In diabetics, HbA1C  $< 7\%$
5. QTc interval normal, with normal defined as  $\leq 0.44s$  ( $\leq 440ms$ )
6. Physical examination: No evidence of organ dysfunction or any clinically significant deviation from normal in physical examination and/or vital signs that in the opinion of the investigator would be a contraindication to randomisation

### 3.4 COHORT II – PREVIOUSLY DIAGNOSED PARTICIPANTS

Previously diagnosed participants will be considered eligible for randomisation in this trial if they fulfil all the inclusion criteria and none of the exclusion criteria as defined below. Blood samples will be taken at screening to assess whether the participant is eligible for randomisation. Eligibility must be assessed within 14 days prior to randomisation.

#### 3.4.1 RANDOMISATION INCLUSION CRITERIA

1. Aged  $\geq 18$  to  $\leq 60$  years old
2. Able to give informed written consent including consent to long-term follow-up
3. Weight  $\geq 50kg^{**}$
4. Confirmed date of diagnosis of primary HIV-1 infection  $\leq 2$  years prior to randomisation
5. Started at least 3-drug ART within a maximum of 4 weeks of diagnosis of the primary HIV-1 infection confirmed by one of the following criteria:

---

†† Results from lab parameters should be within 14 days of randomisation. Repeat tests must be within the ranges as listed above.

\*\* females aged  $< 20$  years of age, and weighing  $< 65kg$  and  $< 168cm$  in height will need to have an estimation of blood volume (EBV)  $> 3500mL$  prior to enrolment. This circumstance is unlikely to arise as most women between the ages of 18 to 20 years would be of child-bearing potential (CBP) and excluded on that basis.

- a. Positive HIV-1 serology within a maximum of 12 weeks of a documented negative HIV-1 serology test result (can include point of care test (POCT))
  - b. A positive p24 antigen result and a negative HIV antibody test
  - c. Negative antibody test with either detectable HIV RNA or proviral DNA
  - d. PHE RITA test algorithm§§ reported as “Incident” confirming the HIV-1 antibody avidity is consistent with recent infection (within the preceding 16 weeks)
  - e. Weakly reactive or equivocal 4th generation HIV antibody antigen test
  - f. Equivocal or reactive antibody test with <4 bands on western blot
6. Currently taking at least 3-drug ART (preferably including raltegravir) and has been on treatment for  $\geq 22$  weeks
  7. Undetectable plasma HIV RNA (<50copies/mL or <200copies/mL for the Taqman Roche 2.0 assay)
  8. Reached an undetectable plasma HIV RNA (<50copies/mL or <200copies/mL for the Taqman Roche 2.0 assay) within 9 months of starting ART and has had no evidence of virological failure as defined by current BHIVA guidelines
  9. Adequate haemoglobin (Hb $\geq 12$ g/dL for males,  $\geq 11$ g/dL for females)
  10. Total blood volume taken in 3 months prior to screening does not exceed 40mL
  11. Willing to be randomised to continue cART alone or cART plus intervention (HIV vaccines plus HDACi)
  12. Willing and able to comply with visit schedule and provide blood sampling

### 3.4.2 RANDOMISATION EXCLUSION CRITERIA

1. Women of child bearing potential (WCBP)\*\*\*
2. In women with intact ovaries and no uterus, any planned egg donation anytime in the future to a surrogate
3. Intention to donate sperm or father a child within 6 months of the intervention
4. Co-infection with hepatitis B (surface antigen positive or detectable HBV DNA levels in blood) or hepatitis C (HCV RNA positive or HCV antigen positive)
5. Any current or past history of malignancy
6. Concurrent opportunistic infection or other comorbidity or comorbidity likely to occur during the trial e.g. past history of ischaemic or other significant heart disease, malabsorption syndromes, autoimmune disease

---

§§ using current cut-offs for optical density as defined by PHE

\*\*\* defined as any female who has experienced menarche and who has not undergone successful surgical sterilisation (hysterectomy or bilateral oophorectomy) or is not postmenopausal (defined as amenorrhoea  $\geq 12$  consecutive months; or women on hormone replacement therapy (HRT) with documented serum follicle stimulating hormone (FSH) level > 35mIU/mL); NB bilateral tubal ligation is reversible, a women with only tubal ligation who does not meet any of the other criteria is considered a WCBP

7. HIV-2 infection
8. Known HTLV-1 co-infection
9. Prior immunisation with any experimental HIV Immunogens (including any component of the vaccines used in the RIVER protocol; simian or human adenoviral vaccine; other experimental HIV vaccines)
10. Current or planned systemic immunosuppressive therapy (inhaled corticosteroids are allowed)
11. Any history of proven thromboembolism (pulmonary embolism or deep vein thrombosis)
12. Any inherited or acquired bleeding diathesis including gastric or duodenal ulcers, varices
13. Concurrent or planned use of any drugs contraindicated with vorinostat i.e. antiarrhythmics; any other drugs that prolong QTc; warfarin, aspirin, sodium valproate
14. Prior intolerance of any of either the components of the vaccine or HDACi,
15. Uncontrolled diabetes mellitus defined as an HBA1C>7%
16. Any congenital or acquired prolongation of the QTc interval, with normal defined as  $\leq 0.44s$  ( $\leq 440ms$ )
17. Participation in any other clinical trial of an experimental agent; participation in an observational study is permitted
18. Allergy to egg
19. History of anaphylaxis or severe adverse reaction to vaccines
20. Planned receipt of vaccines within 2 weeks of the first trial vaccination administered at PR week 00 (including vaccines such as yellow fever; hepatitis B, influenza)
21. Abnormal blood test results at screening including
  - a. Moderate to severe hepatic impairment as defined by Child-Pugh classification
  - b. ALT  $>5xULN$
  - c. Platelets  $<150 \times 10^9/L$
  - d. eGFR  $<60^{+++}$
  - e. uPCR  $>30$  mg/mmol
22. Physical and laboratory test findings: Evidence of organ dysfunction or any clinically significant deviation from normal in physical examination and/or vital signs that the investigator believes is a preclusion from enrolment into the study
23. Active alcohol or substance use that, in the Investigator's opinion, will prevent adequate adherence with study requirements
24. Insufficient venous access that will allow scheduled blood draws as per protocol

---

+++eGFR is calculated using CKD-EPI. Units ml/min/1.73m^2.

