### 3.2 CONSENT PROCESS

Eligible individuals will be flagged by a clinical pathway at each clinical site. This is to incorporate one or more of the following:

- Direct referral from participants following recent diagnosis of HIV
- The study will be advertised through NGO, advocacy partners such as THT, HIV ibase, GMFA and through the CHERUB website
- Virology laboratories where recent infection is identified will notify lead clinical principal investigators to follow up with potentially eligible study participants.

- Clinical referrals pathways will be made from colleagues and from other sites where enrolment is not currently planned - through BHIVA, MRC CTU website and clinical networks

For Cohort II several of the clinical sites participating in RIVER have been recruiting individuals into a separate observational cohort study called HEATHER (funded through NIHR BRC and MRC senior fellowship). The HEATHER (REC reference: 14/WM/1104) study has enrolled individuals with confirmed PHI according to similar criteria to those that define PHI for the RIVER study, all of whom commenced and remained on combination ART from the time of PHI. Individuals who enrol into RIVER Cohort II will cease blood draws and clinical follow up through HEATHER for the time they are in the RIVER protocol. They may return to the HEATHER study after completion of the RIVER protocol.

Written informed consent to enter into the study and be randomised must be obtained from participants after explanation of the aims, methods, benefits and potential hazards of the study and BEFORE any study-specific procedures are performed or any blood is taken for the study (sample participant information leaflet is available in [Appendix VII](#)). Separate Participant Information Leaflets and consent forms have been developed for each cohort.

It must be made completely and unambiguously clear to the participant that they are free to refuse to participate in all or any aspect of the study, at any time and for any reason, without incurring any penalty or affecting their treatment.

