16. Uncontrolled diabetes mellitus defined as an HBA1C>7%
17. Any congenital or acquired prolongation of the QTc interval, with normal defined as  $\leq 0.44s$  ( $\leq 440ms$ )
18. Participation in any other clinical trial of an experimental agent or any non-interventional study where additional blood draws are required; participation in an observational study is permitted
19. Allergy to egg
20. History of anaphylaxis or severe adverse reaction to vaccines
21. Planned receipt of vaccines within 2 weeks of the first trial vaccination administered at PR week 00 (including vaccines such as yellow fever; hepatitis B, influenza)
22. Abnormal blood test results at screening including
  - a. Moderate to severe hepatic impairment as defined by Child-Pugh classification
  - b. ALT >5xULN
  - c. Platelets <150x10^9/L
  - d. eGFR <60\*\*
  - e. uPCR >30 mg/mmol
23. Physical and laboratory test findings: Evidence of organ dysfunction or any clinically significant deviation from normal in physical examination and/or vital signs that the investigator believes is a preclusion from enrolment into the study
24. Active alcohol or substance use that, in the Investigator's opinion, will prevent adequate adherence with study requirements
25. Insufficient venous access that will allow scheduled blood draws as per protocol

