### 4.3 CO-ENROLMENT GUIDELINES

Participants will not be permitted to co-enrol into other interventional studies for the duration of this study. However, there is an expectation that participants will be asked to co-enrol into other observational studies run by the CHERUB network, this participation is allowable.

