## 7.2 OTHER STUDY-SPECIFIC REQUIREMENTS & EXPLORATORY OUTCOMES

### 7.2.1 LARGE VOLUME BLOOD DRAW

The total blood draw over the study for both cohorts is approximately 1500 ml. The largest blood draws occur at randomisation (390ml) and post-randomisation week 16, PR16 (387ml). The UK blood transfusion service ([www.blood.co.uk/giving-blood](http://www.blood.co.uk/giving-blood)) recommends the following in regards to donating blood:

1. Aged 17-65 years and generally in good health.
2. Male donors can donate 4 times in a 12-month period, with each blood donation equal to 470 ml i.e. a total of 1880 ml/annum.
3. Female donors can donate 470mLs every 16 weeks, this is to reduce the risk of iron deficiency anaemia in those still menstruating.

4. Weight must be at least 50 kg, but in females under 20 years of age and weighing <65kg and less than 168cm in height, blood volume needs to be estimated before donation.

In the RIVER protocol, the risks of the blood draws are minimised through the following:

1. Haemoglobin (Hb) within the normal range and weight  $\geq 50$ kg as inclusion criteria for participation; women of CBP are excluded from participation, and none of the women included will be menstruating.
2. Cohort I – Recently diagnosed participants have primary HIV infection and it is most unlikely that there will be any impact on the haematological axis in such participants.
3. Hb checks prior to the larger volume blood draws at randomisation and PR16 i.e. at week 22/screening and PR12 respectively.
4. Participants in Cohort II – Previously diagnosed are excluded if in the 3 months prior to screening  $\geq 40$ ml of blood has been taken.
5. Sites are advised that the participant should not have any large blood draws for 3 months after the last study visit, PR18.

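### Cohort II lacks Cohort I's bar on non-interventional studies that draw blood, and apart from HEATHER nothing limits other observational studies' research blood between screening and PR18

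*Protocol*

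**What the plan says.** Five parts of the Protocol bear on blood taken for other research.

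- **Cohort I, 3.3.2 no. 18.** Besides other trials of an experimental agent, this excludes participation in "any non-interventional study where additional blood draws are required; participation in an observational study is permitted".
- **Cohort II, 3.4.2 no. 17.** The whole item is "Participation in any other clinical trial of an experimental agent; participation in an observational study is permitted". It has no condition about blood.
- **Section 4.3, not limited to a cohort.** Other interventional studies are ruled out, but "there is an expectation that participants will be asked to co-enrol into other observational studies run by the CHERUB network, this participation is allowable".
- **Section 3.2, Cohort II.** HEATHER is an observational cohort from which Cohort II may recruit. "Individuals who enrol into RIVER Cohort II will cease blood draws and clinical follow up through HEATHER for the time they are in" RIVER, and they may return to it afterwards.
- **Section 7.2.1.** This lists how the risk of the large draws is reduced: haemoglobin and weight criteria, haemoglobin checks before the two largest draws (at week 22 or screening, and at PR12), a 40 mL limit for Cohort II in the 3 months before screening, and, for afterwards, "Sites are advised that the participant should not have any large blood draws for 3 months after the last study visit, PR18". Co-enrolment is not on the list.

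**The concern.** The two cohorts follow the same visit pattern after randomisation (Tables 3 and 4), and section 7.2.1 gives one approximate total of 1500 mL for both. The blood burden that could justify the Cohort I clause is therefore much the same in Cohort II, yet the clause appears in only one list and no reason is given. Section 4.3 does not fill the gap, because it permits observational co-enrolment in general terms.

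What is at stake is participant safety and consistent conduct across sites. A site reading 3.4.2 and 4.3 would conclude that a Cohort II participant may give blood to another observational study while RIVER is taking its largest volumes. The same site must exclude a candidate who gave somewhat more than 40 mL in the 3 months before screening.

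**Working it through.** **1. Reproduce the stated total.** The quarterly totals in Table 1 (Cohort I) are 189, 430, 445 and 467 mL.

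189 + 430 + 445 + 467 = 1531 mL, which matches the printed total and the rounded 1500 mL in 7.2.1.

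The visit totals legible in the extracted table add to 1499 mL. The missing 32 mL lies wholly in quarter 3 (413 against 445). It equals one PR11-1 visit of 14 mL routine blood plus the 18 mL assay sample added in version 5.0. That attribution is inferred; the gap is treated as an extraction loss, not an error in the plan.

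**2. Check the two largest draws.**

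- Randomisation: 27 + 80 + 250 + 32 = 389 mL (7.2.1 says 390).
- PR16: 25 + 80 + 250 + 32 = 387 mL (as stated).

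**3. Volume from randomisation to PR18.** Randomisation visit + quarter 3 (PR08-1 to PR12-2) + quarter 4 (PR16 and PR18):

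389 + 445 + 467 = 1301 mL over about 18 to 19 weeks.

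Of this, 445 + 467 = 912 mL falls between PR08-1 and PR18. The total includes the Arm B-only vorinostat virology samples, 3 × 40 = 120 mL, so Arm A gives 1301 − 120 = 1181 mL.

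**4. Cohort II.** Table 2 was not in the text available. Two assumptions are made: the post-randomisation schedule equals Table 1, and the screening draw lies between the Cohort I screening volume (27 mL) and the week 22 volume (34 mL).

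- Total: 1301 + 27 = 1328 mL to 1301 + 34 = 1335 mL.
- With the 40 mL allowed beforehand: 1368 to 1375 mL.

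**5. Compare with the Protocol's own yardstick.** Section 7.2.1 cites blood-donor guidance for men of 470 mL four times a year, 1880 mL in all. The Protocol uses this as a comparison and does not make it a limit.

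- Cohort I, year: 1880 − 1531 = 349 mL below.
- Cohort II, year: 1880 − 1375 = 505 mL to 1880 − 1368 = 512 mL below.
- Cohort I, by quarter against one 470 mL donation: 40, 25 and 3 mL below in quarters 2, 3 and 4. In quarter 3 the 25 mL applies to Arm B; Arm A gives 445 − 120 = 325 mL, which is 145 mL below.

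By the annual comparison there is room; in the quarter holding PR16 and PR18 there is almost none.

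**6. Which rule limits another observational study's draws, and when?**

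| Period | Cohort I | Cohort II |
|---|---|---|
| 3 months before screening | No volume cap found | 40 mL cap (3.4.1 no. 10; 7.2.1 item 4) |
| Screening to PR18 | Exclusion 18, framed as an enrolment criterion | HEATHER only (3.2) |
| 3 months after PR18 | Advice against large draws (7.2.1 item 5) | Same advice |

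The gap is the middle cell for Cohort II, for studies other than HEATHER. The haemoglobin checks in 7.2.1 item 3 and the full blood counts in Table 1 fall in this period. They can detect a fall in haemoglobin but do not restrict what another study takes.

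**7. The 40 mL boundary.** Section 3.4.1 no. 10 requires "Total blood volume taken in 3 months prior to screening does not exceed 40mL", which admits exactly 40 mL. Section 7.2.1 item 4 excludes at 40 mL or more. The two differ only at that value.

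**The case against.** The strongest reply is that the difference between the cohorts has a visible reason. HEATHER draws blood, several RIVER sites recruit to it, and section 3.2 plans for its members to enter Cohort II with sampling suspended. Exclusion 17 turns on participation, so copying the Cohort I clause into it unchanged could exclude those very people. That the omission was deliberate is an inference, but the point stands as a constraint on the fix.

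Four stronger readings might be inferred, and the documents do not support them.

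- *That extra blood is unlimited throughout.* The HEATHER stop, the 40 mL cap beforehand and the advice after PR18 confine the gap to other studies between screening and PR18.
- *That section 4.3 expects studies that draw blood.* It expects co-enrolment in the network's observational studies and is silent on blood.
- *That section 4.3 contradicts Cohort I exclusion 18.* The exclusion itself permits observational studies after its blood-draw clause. The two can be read together, as permission unless extra blood is needed. What is missing is a cross-reference.
- *That the trial period has no safeguard, or that vorinostat delivery will suffer.* Item 3 of 7.2.1 gives haemoglobin checks on study. Haemoglobin at PR08-1 is one of the criteria for starting vorinostat (5.5), so an effect is conceivable. But no document gives the volume, or even the existence, of another blood-drawing study that Cohort II participants would join.

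It is also fair to say that the 1301 mL is the trial's own planned draw and does not measure the extra loss. It shows only the background to which any extra would be added.

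**Conclusion.** The concern holds as a gap in the protocol text. Cohort II lacks the blood-draw clause that Cohort I has, section 4.3 does not supply it, and apart from HEATHER no rule limits other observational studies' research blood between screening and PR18. Section 7.2.1 monitors haemoglobin in that period but does not limit extra draws.

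The background is about 1301 mL of trial blood from randomisation to PR18 in Arm B and about 1181 mL in Arm A. For Cohort II this assumes the Table 1 schedule after randomisation. The size of any additional draw, and its effect on haemoglobin or treatment delivery, cannot be estimated from the documents and is not claimed.

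The matter is one of participant safety and consistency and should be corrected. It has no bearing on the sample size, the type I error or the primary analysis. The 40 mL mismatch is editorial.

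**What to change.** Reconcile 3.2, 3.3.2 no. 18, 3.4.2 no. 17, 4.3 and 7.2.1 so that they state one rule for both cohorts: co-enrolment is allowed only in observational studies that take no additional research blood between screening and PR18. Frame the condition on blood taken during that period and not on membership of another study, so that participants whose other study suspends sampling, as HEATHER does, remain eligible. Let section 4.3 refer to the eligibility items, and add the co-enrolment condition to the list in 7.2.1. Separately, use one form of the 40 mL limit in 3.4.1 no. 10 and 7.2.1 item 4.

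The cost is a wording amendment. For Cohort II, other network studies would defer sampling for about 20 weeks (up to 2 weeks of screening plus 18 weeks after randomisation), as HEATHER already does. The Cohort I period is longer, but exclusion 18 already bars such studies at enrolment, so little is added there.

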## 4 ENROLMENT & RANDOMISATION

Eligibility for enrolment and randomisation will be confirmed by a web-based program. At randomisation eligible participants will be randomised to two parallel groups in a 1:1 ratio (see [Figure 1](#) and [Figure 2](#)). Randomisation lists will be computer-generated based on random permuted blocks and will be performed by the RIVER Co-ordinating Centre staff on receipt of a completed randomisation CRF. Randomisation will be stratified by Cohort I and Cohort II.

### 4.1 ENROLMENT PRACTICALITIES

Participants in Cohort I – Recently diagnosed must be enrolled into the study **within 4 weeks** of a confirmed diagnosis of primary HIV-1 infection. A screening visit will be conducted prior to enrolment where laboratory tests will be conducted in order to determine participant eligibility for enrolment at week 0 (see [Section 6.1.1](#)).

### 4.2 RANDOMISATION PRACTICALITIES

Screening for randomisation:

- For participants in Cohort I – Recently diagnosed  
Blood samples will be taken at week 22 (or later if repeat bloods are required) to assess whether the participant can proceed to randomisation.
- For participants in Cohort II – Previously diagnosed  
Blood samples will be taken at screening to assess whether the participant can proceed to randomisation.

As soon as results from the week 22 or screening visits are known and eligibility for randomisation can be determined, a completed CRF should be submitted to the RIVER Co-ordinating Centre. The result of the randomisation will determine where the participant's first visit post-randomisation will take place (at Royal Free Hospital or at recruiting site).

Further details on the process of randomisation can be found in [Section 9.1](#).

